3.3. Patient Selection

3.3.1. Inclusion Criteria

To be eligible for inclusion into this study, each patient must fulfil the following inclusion criteria:

1. Male or female aged ≥ 18 years.
2. Patients with moderate to severe dry eye characterized by the following clinical features:
 - a. Corneal and/or conjunctival staining with fluorescein using National Eye Institute (NEI) grading system > 3;
 - b. Symptom Assessment in Dry Eye (SANDE) questionnaire > 25 mm;
 - c. Schirmer test I (without anaesthesia) > 2 mm < 10 mm/5 minutes;
 - d. Tear film break-up time (TFBUT) < 10 seconds in the worse eye.
3. The same eye (eligible eye) must fulfill all the above criteria.
4. Patients diagnosed with dry eye at least 6 months before enrolment (current use or recommended use of artificial tears for the treatment of dry eye).
5. (For patients already enrolled into the study under protocol 1) : Best corrected distance visual acuity (BCDVA) score of ≥ 0.1 decimal units in both eyes at the time of study enrolment.
5a. (Revised version in protocol version 2.0) : Best corrected distance visual acuity (BCDVA) score of ≥ 0.1 decimal units (20/200 Snellen value) in both eyes at the time of study enrolment.
6. If a female with childbearing potential, have a negative pregnancy test.
7. (For patients already enrolled into the study under protocol 1) : Only patients who satisfy all informed consent requirements may be included in the study. The patient and/or his/her legal representative must read, sign and date the informed consent document before any study-related procedures are performed. The informed consent form (ICF) signed by patients and/or legal representative must have been approved by the IRB/IEC for the current study.
7a. (Revised version in protocol version 2.0) : Only patients who satisfy all informed consent requirements may be included in the study. The patient and/or his/her legal representative must read, sign and date the informed consent document before any study-related procedures are performed. The informed consent form (ICF) signed by patients and/or legal representative must have been approved by the IRB for the current study.

This document is confidential.

8. Patients must have the ability and willingness to comply with study procedures.

9. (New criteria added in protocol version 2.0) Primary Sjögren's Syndrome Patients: patients with a documented diagnosis of Primary Sjögren's Syndrome according the American-European Consensus Group Sjögren's Syndrome Criteria (Appendix 3 of the study protocol; must meet either 4 out of 6 total criteria OR 3 out of 4 signs). Note: Subjects who are on systemic (oral) therapy for the treatment of Sjögren's Syndrome must be on stable systemic treatment defined as the same treatment for the immediately prior 90 days.

3.3.2. Exclusion Criteria

Patients who meet any of the following criteria are NOT eligible for inclusion in the study:

1. Inability to speak and understand the local language sufficiently to understand the nature of the study, to provide written informed consent, and to allow the completion of all study assessments.
2. Evidence of an active ocular infection, in either eye.
3. Presence of any other ocular disorder or condition requiring topical medication during the entire duration of study.
4. (For patients already enrolled into the study under protocol 1) : History of severe systemic allergy or ocular allergy (including seasonal conjunctivitis) or chronic conjunctivitis and/or keratitis other than dry eye.
- 4a. (Revised version in protocol version 2.0) : History of severe systemic allergy or severe ocular allergy (including seasonal conjunctivitis) or chronic conjunctivitis and/or keratitis other than dry eye.
5. Intraocular inflammation defined as Tyndall score > 0.
6. History of malignancy in the last 5 years.
7. Systemic disease not stabilized within 1 month before screening visit (e.g., diabetes with glycemia out of range, thyroid malfunction.) or judged by the investigator to be incompatible with the study (e.g., current systemic infections) or with a condition incompatible with the frequent assessment required by the study.
8. Patient had a serious adverse reaction or significant hypersensitivity to any drug or chemically related compounds or had a clinically significant allergy to drugs, foods, amide local anesthetics or other materials including commercial artificial tears, in particular commercial artificial tears containing carboxymethylcellulose (in the opinion of the investigator).
9. Females of childbearing potential (those who are not surgically sterilized or post-menopausal for at least 1 year) are excluded from participation in the study if they meet any one of the following conditions:
 - a. are currently pregnant or;
 - b. have a positive result at the urine pregnancy test (Screening/Baseline day 1) or;
 - c. intend to become pregnant during the study treatment period or;
 - d. are breast-feeding or;
 - e. are not willing to use highly effective birth control measures, such as: hormonal contraceptives - oral, implanted, transdermal, or injected - and/or mechanical barrier methods - spermicide in conjunction with a barrier such as a condom or diaphragm or intrauterine device - during the entire course of and 30 days after the study treatment periods.

This document is confidential.

10. Any concurrent medical condition that, in the judgment of the PI, might interfere with the conduct of the study, confound the interpretation of the study results, or endanger the patient's well being.
11. Use of topical cyclosporine, topical corticosteroids or any other topical drug for the treatment of dry eye in either eye within 30 days of study enrolment.
12. Contact lenses or punctum plug use during the study (previous use not an exclusion criteria but must be discontinued at the pre-screening visit).
13. History of drug addiction or alcohol abuse.
14. Any prior ocular surgery (including refractive palpebral and cataract surgery) if within 90 days before the pre-screening visit.
15. (For patients already enrolled into the study under protocol 1) : Participation in a clinical trial with a new active substance.
- 15a. (Revised version in protocol version 2.0) : Participation in a clinical trial with a new active substance including medical devices during the past 60 days.
16. Participation in another clinical trial study at the same time as the present study.

3.4. Determination of Sample Size

In order to evaluate the minimal effective daily dose of rhNGF eye drops, a Williams design has been chosen [1] [2]. For this study three treatment groups have been considered: rhNGF eye drops solution 20 µg/mL TID; rhNGF eye drops solution 20 µg/mL BID plus vehicle eye drop solution SID; vehicle eye drop solution TID.

To this purpose, the sample size has been determined applying the formula reported in the publication Chow et al., 2008 at page 301 [3]

The sample size calculation for the primary variable is based on the following assumptions:

- The probability level (α) for one-sided test is set at 0.025 (see table 12.1.2 at page 298 in Chow et al., 2008[3]) and the power level at approximately 90%.
- DELTA, in change from baseline between treatments, of 5.3 and Standard Deviation for DELTA of 10.78. Both DELTA parameters are derived from results of co-variance analysis obtained from study NGF0216 in the subset of hyposecretive patients (i.e., excluding "evaporative-only" patients).

According to this calculation, 87 patients per treatment group (for a total of 261 patients) are adequate to observe the planned difference assumed for the minimum effective daily dose. Assuming a drop-out of about 15%, a total of 300 is the target number of patients proposed to be enrolled.

The inclusion of at least 60 subjects with documented diagnosis of Primary Sjögren's Syndrome within the planned 300 patients will have no impact on the initial study assumptions (Standard Deviation of 10.78 and DELTA of 5.3 mm) because the patients could have been enrolled based on the previous criteria on which sample size was based. Moreover, a similar prevalence of patients with Primary Sjögren's Syndrome has already been reported in the NGF0216 medical history (~25% of patient the FAS population).

Impact on the power of the study due to stopping enrollment in the study to 261 randomized subjects:

This document is confidential.

With 261 patients randomized, assuming a drop out rate of 15%, only 228 patients in total (76 patients by group) are considered adequate to observe the planned difference assumed for the minimum effective daily dose.

With 76 patients by group, with a DELTA, in change from baseline between treatments of 5.3 and Standard Deviation for DELTA of 10.78, the power to detect a difference will be at least 85%.

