5.4. Full Analysis Set

Full Analysis Set (FAS) will consist of all patients randomized who took at least one dose of IP and who have at least one post-baseline efficacy measurement for the primary endpoint. This analysis set will be used for the primary efficacy analysis. Patients will be analyzed according to the randomized treatment.

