6.3. Missing Data

6.3.1. Missing Data for Efficacy

For Schirmer test I, Schirmer test II, SANDE, fluorescein staining and TFBUT, the LOCF method will be used for imputing missing data in the FAS set at Week 4.

For missing data at Week 4, the data from the previous visit (Week 2 or early discontinuation visit if during treatment period) will be used to estimate the missing value. If a patient has missing data for all post baseline visits, baseline will be carried forward (this cannot happen for the primary end-point because of the FAS definition).

Several sensitivity analyses will be performed concerning the primary analysis in case of many missing values (decision to be made at the final blind Data Review Meeting, before data base lock).

The following strategies will be applied: (a) an analysis restricted to the complete cases (only subjects having a full data set for the primary outcome will be considered); (b) an analysis of repeated measures performed on all subjects having at least one post-baseline efficacy measurement and assuming that missing data are distributed as missing at random (see Appendix 1 for the SAS code); (c) an analysis considering the worst case method (the worst possible value of the scale is assigned to missing values).

For IDEEL and EQ-5D-3L questionnaires, missing data will be imputed according to the questionnaire manuals.

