8.1. Primary Efficacy Endpoint and Analysis

The primary efficacy endpoint is the change from baseline in Schirmer test I (without anesthesia) versus Week 4. The primary analysis is based on the FAS population. Missing data will be replaced by means of the Last Observation Carried Forward (LOCF) method.

The Schirmer test I will be summarized using descriptive statistics for continuous variables by treatment and visit. The change from baseline value will also be summarized for all post-baseline visits. The same summary analysis will be provided after pooling the treated patients (20 µg/mL BID arm and 20 µg/mL TID) together. Comparison (descriptive in nature) of the change from baseline of each treatment versus placebo will be performed by means of a t-test at each timepoint.

The primary analysis will be performed by means of an analysis of variance including only treatment as main factor followed by pre-planned comparisons from Vehicle and rhNGF dosages according to Williams' procedure.

The first comparison will compare the rhNGF TID dose to the Placebo using Williams test.

In case of significant result then the rhNGF BID dose will be compared to the Placebo; if the result is not significant then the test will be stopped.

Description of the Williams' Test:

μ_0 = Effect of Placebo

μ_1 = Effect of rhNGF BID

μ_2 = Effect of rhNGF TID

Hypotheses:

$H_0: \mu_0 = \mu_1 = \mu_2$

$H_1: \mu_0 <= \mu_1 \leq \mu_2$

The test develops into two phases:

* First step

Starting from the observed means X_i , determine the maximum likelihood estimates M_i (corrected mean of group i after amalgamation) under the alternative hypothesis.

If X_i satisfies the inequalities written in H_1 then $M_i = X_i$

Otherwise pool any adjacent violators into the same value:

$M_i = (n_i * X_i + n_{i+1} * X_{i+1}) / (n_i + n_{i+1})$ where n_i = sample size of group i.

The process is repeated until the means are completely ordered.

This document is confidential.

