*** Second step**

Calculate the test statistic given by
 $T_k = (M_k - X_0) / s * \sqrt{1/n_0 + 1/n_k}$

where s = root mean square error and X_0 is the observed mean in the placebo group.

The fact that the k th dose level is the minimum effective dose is concluded if $T_j > t_{j,\alpha}$ for all $j \geq k$ where the $t_{j,\alpha}$ values are the critical values reported by Williams [2].

The Schirmer test I values will be also listed.

An explorative sensitivity analysis of the primary endpoint will be conducted including in the analysis of variance the absence/presence of diagnosis of Primary Sjögren's Syndrome and its interaction with treatments as covariates. If the interaction term is statistically significant (at the 0.10 level given its explorative nature), the treatment effects within patients with and without Primary Sjögren's Syndrome will be provided.

For patients already enrolled in the study, the assignment to a strata will be based on Medical history form.

If "Primary Sjogren" is recorded in the Medical condition of the Medical history form then the patient will be assigned to "Presence of Primary Sjogren"; if only "Sjogren" is recorded then the patient will be assigned to "Absence of Primary Sjogren". In all other cases, the patient will be assigned to "Absence of Primary Sjogren".

In order to assess the robustness of results of primary analysis, the Schirmer test I will be also evaluated by means of non parametric Fisher's exact test after applying the following categorization at week 4:

- A patient is defined as "Responder" if the Schirmer test I value at week 4 is greater than 10 mm/5 minutes;
- A patient is defined as "Non responder" if the Schirmer test I value at week 4 is lower or equal than 10 mm/5 minutes.

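### SAP 3.4: a 15% loss from 261 leaves 222 patients (74 per group), not 228 (76), and the stated 85% power floor is then narrowly missed at 84.9%

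*SAP*

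**What the plan says.** SAP section 3.4 repeats the protocol's calculation (protocol 9.1): difference 5.3, SD 10.78, one-sided alpha 0.025 and power of approximately 90% give 87 per group, 261 in total. It then adds: "Assuming a drop-out of about 15%, a total of 300 is the target number of patients proposed to be enrolled".

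The SAP alone goes on to describe the effect of stopping at 261 randomized: "With 261 patients randomized, assuming a drop out rate of 15%, only 228 patients in total (76 patients by group") are taken as adequate for the planned difference. With 76 per group and the same difference and SD, "the power to detect a difference will be at least 85" per cent.

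Three other places bear on how to read this:
- SAP section 2 gives the status at 9 March 2020: 256 randomized, of whom 185 had completed, 44 had terminated early and 27 were ongoing, with 5 more not yet randomized.
- SAP 5.4 admits to the full analysis set (FAS) treated patients "who have at least one post-baseline efficacy measurement for the primary endpoint".
- SAP 6.3.1 handles a missing Week 4 value by last observation carried forward (LOCF): "the data from the previous visit (Week 2 or early discontinuation visit if during treatment period) will be used to estimate the missing value".

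**The concern.** The new count is a one-step calculation from two figures in the same sentence, and it does not come out. The power statement is then computed at that count and worded as a lower bound, so an overstated count can turn a bound that is just missed into one that appears to be met.

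This is the SAP's only statement of what early stopping cost in power. A reader weighing a non-significant result will go to it, so its n should follow from its own dropout rate and its bound should hold at that n.

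**Working it through.** **Inputs (all SAP 3.4):** difference d = 5.3; SD s = 10.78; one-sided alpha 0.025; 87 per group originally; 261 randomized; dropout 15%. Groups are taken as equal (1:1:1, SAP 3.5).

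**1. Reproduce the original 87.** The cited textbook formula and critical-value table are not in the documents. The usual formula is n per group = 2s²(z_α + z_power)²/d².
- With z_α = 1.96 and power 90%: 2 × 116.2084 × (1.96 + 1.2816)²/28.09 = 86.94, so 87. This matches the SAP.
- With a critical value of 1.99 it would be 88.56, so 89, which does not match.

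The value 1.96 is therefore inferred, because it reproduces the stated figure.

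**2. Count after dropout.**
- 261 × (1 − 0.15) = 221.85, so 222, or 74 per group.
- Loss implied by the SAP's figure: 1 − 228/261 = 12.6%.
- The SAP's figure reproduces as 87/1.15 = 75.65, rounded up to 76, and 76 × 3 = 228. The likely cause is dividing by 1.15 instead of multiplying by 0.85.

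**3. Power for a single comparison with vehicle.** Normal formula: Φ(d/(s√(2/n)) − 1.96). The last column uses the noncentral t distribution with 3n − 3 error degrees of freedom.

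| n per group | d/(s√(2/n)) | Power, normal | Power, t |
|---|---|---|---|
| 74 | 2.991 | 84.9% | 84.6% |
| 75 | 3.011 | 85.3% | 85.0% |
| 76 | 3.031 | 85.8% | 85.5% |
| 87 | 3.243 | 90.0% | 89.8% |

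So the SAP's power holds at its stated 76. It fails at 74 under both calculations. Solving the formula for 85% gives 74.29, so 75 per group are needed. The difference between 76 and 74 is 85.79 − 84.86 = 0.93 points.

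**4. Check against the reported status (SAP 2).** With 44 early terminations already recorded, at most 185 + 27 + 5 = 217 of 261 can complete the study to Week 16. The termination proportion was 44/256 = 17.2%. Neither 222 nor 228 can therefore be the number of study completers.

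**5. Check against the analysis set.** The primary endpoint is at Week 4, and a patient who leaves after one post-baseline Schirmer I value stays in the FAS through LOCF. If all 261 had such a value, the analysed number would be 87 per group, with power of about 90% before any dilution of the effect by carried-forward values.

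**The case against.** The strongest reply is that this changes nothing that matters. The shortfall is 0.14 points, a fair rewording is still about 85%, and it depends on a critical value inferred from the stated 87. Most of that stands as a limit on the size of the point. It does not rescue the sentence: the count is wrong whatever the formula, a floor stated as at least 85% should hold at the correct count, and a larger critical value would only widen the gap (84.1% at 74 per group with 1.99).

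A second reply is that the original target shows the same habit, since 261 × 1.15 = 300. That is so, but the original text says about 15% and approximately 90%. At exactly 15% loss, 300 gives 255, or 85 per group and about 89% power, which fits that wording. The sentence on 261 gives 15% without qualification.

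A reader might also infer that the SAP promises 85% at each step of the Williams procedure and breaks that promise. In SAP 8.1, "The first comparison will compare the rhNGF TID dose to the Placebo using Williams test", and then "In case of significant result then the rhNGF BID dose will be compared to the Placebo". But section 3.4 speaks only of detecting a difference and makes no promise for each step. Power for each step would also need dose-response assumptions that the documents do not give. Naming the comparison is a useful clarification; its absence is not a contradiction.

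**Conclusion.** The stated count is wrong as written: 15% of 261 lost leaves 222 (74 per group), not 228 (76). On the SAP's inputs, single-comparison power is then 84.9% (84.6% with t), just under the stated floor. The overstatement is 6 patients and about 0.9 points. This rests on equal groups, the inferred value 1.96, and reading the power as that of one comparison with vehicle.

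Two stronger readings are not supported. One is that the trial is materially underpowered: the corrected figure is still about 85%, and no test, alpha, dataset or enrolment is affected. The other is that 222 is the number who will complete or be analysed. The reported terminations rule out 222 completers, and the FAS with LOCF means that the Week 4 number is not fixed by completion and may be as high as 87 per group.

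**What to change.** In the closing paragraphs of SAP 3.4:
- Replace 228 (76 per group) with 222 (74 per group), presented as the arithmetic result of the assumed 15%. Change the 76 that opens the following power sentence to 74.
- Replace the lower bound of 85% with: *about 85% (84.9%) for a single comparison with vehicle at one-sided 0.025*.
- Add a note: *The number analysed at Week 4 is not fixed by study completion. The FAS with LOCF keeps patients with one post-baseline Schirmer I value, so it may be as large as 87 per group (about 90% power, before any dilution of the effect by LOCF).*

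Do not write that 222 patients would complete, because the counts in SAP section 2 allow at most 217. The original target of 300 needs no change.

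The cost is text only. The stated n and power become slightly less favourable.

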3.5. Treatment Assignment & Masking

Eligible patients will be randomized in a 1:1:1 ratio to either rhNGF eye drops solution 20 µg/mL TID (100 patients) or rhNGF eye drops solution 20 µg/mL BID plus vehicle eye drop solution SID (100 patients) or vehicle eye drop solution TID (100 patients).

Following amendment n° 1 to the protocol, randomization will be stratified according to absence/presence of a documented diagnosis of Primary Sjögren's Syndrome.

The study was ongoing at the time of amendment and at the beginning of September 135 patients had already been randomized. The randomization list generated on March 22, 2019 will be stopped when the last randomization number used will be at the end of a block. Moving forward, the replacement list will be used. According to the amendment n° 1, the replacement randomization schedule will be stratified according to absence/presence of a documented diagnosis of Primary Sjögren's Syndrome.

Each randomized patient after amendment will be allocated with randomization number, according to the stratified randomization list using an Interactive Web Response System (IWRS). Drop outs after randomization will not be replaced.

Randomization lists as well as associated kit numbers will be generated by a member of Syneos Health Biostatistics department, not involved in the conduct of the study.

Patients will be assigned to treatment in numerical order. A tear-off label from the kit box, with the kit number, will be attached to the investigational product dispensing log.

The enrollment of patients will be scheduled in order to assure an inclusion of approximately 240 patients without Primary Sjögren's Syndrome diagnosis and at least 60 patients with Primary Sjögren's Syndrome.

For patients already enrolled in the study, the assignment to a strata will be based on Medical history form (see section 8.1).

The identity of the treatments will remain unknown to the patient, Investigator, site staff and Sponsor's clinical research personnel until the study is unmasked for the final statistical analysis (after data base lock) except in case of specific events that will require unmasking of the patient.

The vials containing rhNGF (20 µg/mL) or vehicle will be identical in appearance, and the contents of the vials will be indistinguishable. All staff directly involved in the analysis of study results will remain masked to treatment assignments while the study is in progress.

If the Investigator becomes unmasked for any reason, this information will be recorded on source data and in the electronic case report form (eCRF) of the study, specifying the date and the reason. Unmasking events will be recorded and reported in the final study report.

